10.4 Safety Analysis

10.4.1 Safety analysis for Part A

All safety analyses will be conducted based on data from the corresponding OLE Safety Period for Part A in the OLE-SS for Part A.

The overall long-term safety profile of study drug will be assessed in terms of the following safety and tolerability endpoints:

- Treatment-emergent adverse events (TEAEs)
- Clinical laboratory values
- Standard 12-lead ECGs
- Vital signs
- Pulse oximetry

In the AE summary tables, AE data from the OLE Safety Period for Part A may be displayed side-by-side with the AE data from study 445-106 Part B.

Only descriptive analysis of safety will be performed, and no statistical testing will be performed.

10.4.1.1 Adverse Events

For analysis purposes, AEs will be classified as pretreatment AEs, TEAEs, or post-treatment AEs, defined as follows:

- **Pretreatment AE:** any AE that occurred before the first dose date of study drug in the OLE Safety Period for Part A.
- **TEAE:** any AE that worsened (either in severity or seriousness) or that was newly developed at or after the first dose date of study drug through the end of the OLE Safety Period for Part A.
- **Post-treatment AE:** any AE that worsened (either in severity or seriousness) or that was newly developed after the OLE Safety Period for Part A.

For AEs with completely missing or partially missing start dates, if there is no clear evidence that the AEs were pretreatment or post-treatment, the AEs will be classified as TEAEs.

Details for imputing missing or partial start dates of adverse events are defined in Appendix D.

An overview of all TEAEs during OLE Safety Period for Part A will be provided with the following categories:

- Number of TEAEs (total number of TEAEs only)
- Subjects with any TEAEs
- Subjects with TEAEs by strongest relationship
- Subjects with TEAEs by maximum severity
- Subjects with TEAEs leading to study drug discontinuation (discontinuation of any study drug)
- Subjects with TEAEs leading to study drug interruption (interruption of any study drug)
- Subjects with grade 3/4 TEAEs
- Subjects with related TEAEs
- Subjects with serious TEAEs
- Subjects with related serious TEAEs
- Subjects with TEAEs leading to death

The frequency counts and percentages as well as the exposure adjusted event rate will be presented for the above overview table. The exposure adjusted rate will not be presented for strongest relationship and maximum severity categories.

The following summary tables of TEAEs during OLE Safety Period will be presented:

- All TEAEs
- TEAEs leading to treatment discontinuation
- TEAEs leading to treatment interruption
- Serious TEAEs
- TEAEs leading to death
- Grade 3/4 TEAEs
- TEAEs by strongest relationship
- TEAEs by maximum severity
- Related TEAEs
- Related serious TEAEs

Summaries will be presented by MedDRA SOC and PT using frequency counts and percentages (i.e., number and percentage of subjects with an event) and the exposure adjusted event rate (except for summary by strongest relationship and maximum severity). When summarizing the number and

percentage of subjects, subjects with multiple occurrences of the same AE or a continuing AE will be counted once and only the maximum severity level will be presented in the severity summaries, and the strongest relationship level will be presented in the relationship summaries.

Additional summary table in which the frequency counts and percentages as well as the exposure adjusted event rate will be presented for TEAEs during the OLE Safety Period for Part A:

- All TEAEs by PT

All AEs in in Part A, including pretreatment AEs, TEAEs, and post-treatment AEs, will be presented in an individual subject data listing based on the OLE All Subjects Set for Part A. In addition, a listing containing individual subject adverse event data for TEAEs leading to treatment discontinuation, TEAEs leading to treatment interruption, Grade 3/4 TEAEs, SAEs and all deaths will be provided separately, with a flag indicating the TEAE status for SAEs and deaths.

10.4.1.2 Clinical Laboratory

For the treatment-emergent laboratory assessments, the observed values and change from baseline values of the continuous hematology, coagulation and chemistry results will be summarized in SI units at each visit during the OLE Safety Period for Part A.

The number and percentage of subjects with selected test values meeting at least 1 threshold analysis criterion event during the OLE Safety Period for Part A will be summarized. The threshold analysis criterion shift from baseline will also be summarized for selected laboratory parameters. The threshold analysis criteria are provided in Appendix E.

For selected LFT laboratory tests (alanine transaminase [ALT], aspartate transaminase [AST], alkaline phosphatase [ALP], and total bilirubin), a scatter plot of the maximum treatment-emergent value versus the baseline value corresponding to \times ULN (upper limit of normal) will be presented. Further, a scatter plot of the maximum treatment-emergent value of ALT and AST, separately, versus the maximum treatment-emergent value of total bilirubin corresponding to \times ULN will also be presented.

Results of urinalysis and the positive urine/serum pregnancy test will be listed in individual subject data listings only. For positive serum pregnancy listing, subjects with serum HCG which elevated above the upper limit of normal will be selected.

In addition, a listing containing individual subject hematology, chemistry, and coagulation values will be provided. This listing will include data from both scheduled and unscheduled visits.

10.4.1.3 Electrocardiogram

For the following ECG measurements during the OLE Safety Period for Part A, a summary of observed values and change from baseline values will be provided at each visit for the following ECG measurements (in msec): RR interval, PR interval, QT interval, QTcF interval, QRS duration, and Heart Rate (beats per minute).

The number and percentage of subjects meeting at least 1 threshold analysis criterion during the OLE Safety Period for Part A will be summarized. The threshold analysis criteria are provided in Appendix E.

In addition, a listing containing individual subject ECG values will be provided. This listing will include data from both scheduled and unscheduled visits.

10.4.1.4 Vital Signs

For the vital signs measurements during the OLE Safety Period for Part A, the observed values and change from baseline values will be summarized at each visit. The following vital signs parameters will be summarized: systolic and diastolic blood pressure (mm Hg), body temperature (°C), pulse rate (beats per minute), and respiratory rate (breaths per minute).

The number and percentage of subjects meeting at least 1 threshold analysis criterion during the OLE Safety Period for Part A will be summarized. The threshold analysis criteria are provided in Appendix E.

In addition, a listing containing individual subject vital sign values will be provided. This listing will include data from both scheduled and unscheduled visits.

10.4.1.5 Pulse Oximetry

For the percent of oxygen saturation measurements using pulse oximetry during the OLE Safety Period for Part A, a summary of observed values and change from baseline values will be provided at each visit.

The number and percentage of subjects with shift change from baseline (normal/missing and low according to the reference range) to the lowest percent of oxygen saturation during the OLE Safety Period for Part A will be summarized. The reference range for normal oxygen saturation is specified as >95%, and <=95% for low oxygen saturation.

10.4.1.6 Ophthalmologic Examinations

The ophthalmologic examination results will be presented in individual subject data listings.

10.4.1.7 Physical Examination

No tables/figures/listings will be provided for PE data.

10.4.1.8 COVID-19 Impacted Visits

A listing containing subjects' visits impacted due to COVID-19 will be provided.

10.4.1.9 Supportive Safety Analysis

10.4.1.9.1 Adverse Events of Special Interest

For this study, elevated transaminases events and rash events, as determined by MedDRA Preferred Terms in the respective Customized MedDRA Queries (CMQ), are considered as adverse events of special interest.

For treatment-emergent elevated transaminases events and rash events, the following categories will be summarized:

- Subjects with events
- Subjects with events by maximum severity
- Subjects with events leading to treatment discontinuation
- Subjects with events leading to treatment interruption
- Subjects with serious events

- Subjects with related serious events
- Subjects with events leading to death
- Duration of events
- Time-to-onset of first event (with the first dose date of study drug in Part A as the reference while calculating time-to-onset)

In addition, for treatment-emergent rash events, the above categories will be summarized for the following subgroups:

- Sex (male, female)

10.4.2 Safety analysis for the OLE study

All safety analyses will be conducted based on the OLE Safety Period for subjects in the OLE-SS.

The overall long-term safety profile of study drug will be assessed in terms of the following safety and tolerability endpoints:

- Treatment-emergent adverse events (TEAEs)
- Clinical laboratory values
- Standard 12-lead ECGs
- Vital signs
- Pulse oximetry

In the AE summary tables, AE data from the OLE Safety Period may be displayed side-by-side with the AE data from the parent study 445-106 Part B.

Only descriptive analysis of safety will be performed, and no statistical testing will be performed.

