8.1 Part A

8.1.1 Inclusion Criteria

1. Subject (or his or her legally appointed and authorized representative) will sign and date an ICF, and, when appropriate, an assent form.
2. Willing and able to comply with scheduled visits, treatment plan, study restrictions, laboratory tests, contraceptive guidelines, and other study procedures.
3. Did not withdraw consent from the parent study.
4. Meets at least 1 of the following criteria:
 - Completed study drug treatment in the parent study, or
 - Had study drug interruption(s) in the parent study, but did not permanently discontinue study drug, and completed study visits up to the last scheduled visit of the Treatment Period of the parent study.
5. Willing to remain on a stable CF treatment regimen (as defined in Section 9.5) through completion of study participation.

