8.1.2 Exclusion Criteria

1. History of any comorbidity that, in the opinion of the investigator, might confound the results of the study or pose an additional risk in administering study drug to the subject.
2. Pregnant or breast-feeding females. Female subjects must have a negative pregnancy test at the Part A Day 1 Visit before receiving the first dose of study drug.
3. History of drug intolerance in the parent study that would pose an additional risk to the subject in the opinion of the investigator (e.g., subjects with a history of allergy or hypersensitivity to the study drug).
4. Current participation in an investigational drug study other than the parent study, or the current study. Participation in a noninterventional study and screening for another Vertex study is permitted.

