9.3 Analysis Period for Final Analysis

OLE Efficacy Period: Time from the first dose of study drug in the OLE study to the last efficacy assessment, which may be collected up to OLE Part B Week 96 Visit or the earlier of Day 1345 and the end of study participation if subject does not have the OLE Part B Week 96. This analysis period will be used with the OLE-FAS to analyze efficacy data in the Week 144 IA and the final analysis.

OLE Safety Period: Time from the first dose of study drug in the OLE study to 28 days after the last dose of the study drug in the OLE study or to the completion date of study participation (as defined in Section 9.1.5 of the CSP), whichever occurs first.

The completion date of study participation will be obtained from the end of study page of the eCRF.

The **OLE Treatment-emergent (TE) Period** is same as the OLE Safety Period.

The OLE Cumulative TC Efficacy Period: For subjects who enrolled in the OLE study, the time from the first dose of study drug in the parent study (445-106 Part B) until the last efficacy assessment in the OLE study, which may be collected up to the Part B Week 96 Visit or the earlier of Day 1345 and the end of study participation if subject does not have the Part B Week 96 Visit. For subjects who did not enroll in the OLE study and were enrolled and received study drug in the parent study, definition of this analysis period is the same as the parent study efficacy period.

The Cumulative TC Efficacy periods will be used with the Cumulative TC sets for analysis of PEx data.

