10.4.2.1 Adverse Events

For analysis purpose, AEs will be classified as pretreatment AEs, TEAEs, or post-treatment AEs, defined as follows:

- **Pretreatment AE:** any AE that occurred before the first dose date of study drug in the OLE Safety Period.
- **TEAE:** any AE that worsened (either in severity or seriousness) or that was newly developed at or after the first dose date of study drug through the end of the OLE Safety Period.
- **Post-treatment AE:** any AE that worsened (either in severity or seriousness) or that was newly developed after the OLE Safety Period.

For AEs with completely missing or partially missing start dates, if there is no clear evidence that the AEs were pretreatment or post-treatment, the AEs will be classified as TEAEs.

Details for imputing missing or partial start dates of adverse events are defined in Appendix D.

An overview of all TEAEs during OLE Safety Period will be provided with the following categories:

- Number of TEAEs (total number of TEAEs only)

- Subjects with any TEAEs
- Subjects with TEAEs by strongest relationship
- Subjects with TEAEs by maximum severity
- Subjects with TEAEs leading to study drug discontinuation (discontinuation of any study drug)
- Subjects with TEAEs leading to study drug interruption (interruption of any study drug)
- Subjects with grade 3/4 TEAEs
- Subjects with related TEAEs
- Subjects with serious TEAEs
- Subjects with related serious TEAEs
- Subjects with TEAEs leading to death

The frequency counts and percentages as well as the exposure adjusted event rate will be presented for the above overview table. The exposure adjusted rate will not be presented for strongest relationship and maximum severity categories.

The following summary tables of TEAEs during OLE Safety Period will be presented:

- All TEAEs
- TEAEs leading to treatment discontinuation
- TEAEs leading to treatment interruption
- Serious TEAEs
- TEAEs leading to death
- Grade 3/4 TEAEs
- TEAEs by strongest relationship
- TEAEs by maximum severity
- Related TEAEs
- Related serious TEAEs

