Summaries will be presented by MedDRA SOC and PT using frequency counts and percentages (i.e., number and percentage of subjects with an event) and the exposure adjusted event rate (except for summary by strongest relationship and maximum severity). When summarizing the number and percentage of subjects, subjects with multiple occurrences of the same AE or a continuing AE will be counted once and only the maximum severity level will be presented in the severity summaries, and the strongest relationship level will be presented in the relationship summaries.

Additional summary table in which the frequency counts and percentages as well as the exposure adjusted event rate will be presented for TEAEs during the OLE Safety Period:

- All TEAEs by PT

All AEs, including pretreatment AEs, TEAEs, and post-treatment AEs, will be presented in an individual subject data listing based on the OLE All Subjects Set. In addition, a listing containing individual subject adverse event data for TEAEs leading to treatment discontinuation, TEAEs leading to treatment interruption, Grade 3/4 TEAEs, SAEs and all deaths will be provided separately, with a flag indicating the TEAE status for SAEs and deaths.

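### If extension adverse events are shown beside the parent study, three summaries have no exposure-adjusted rate and the parent column is not limited to subjects who rolled over

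*SAP*

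**What the plan says.** The SAP permits, without requiring, a two-study display of adverse events. For the whole extension, 10.4.2 states that "AE data from the OLE Safety Period may be displayed side-by-side with the AE data from the parent study 445-106 Part B". For Part A, 10.4.1 states that "AE data from the OLE Safety Period for Part A may be displayed side-by-side with the AE data from study 445-106 Part B". Neither section attaches a condition on follow-up time or on which parent-study subjects are shown.

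Exposure is handled in most of the tables. In 10.4.2.1, "The frequency counts and percentages as well as the exposure adjusted event rate will be presented for the above overview table". The tables by system organ class and preferred term, and the table by preferred term alone, also carry the rate. The exception is explicit: "The exposure adjusted rate will not be presented for strongest relationship and maximum severity categories". It is repeated for the system-organ-class tables, and 10.4.1.1 has the same exception for Part A.

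The special-interest summaries in 10.4.1.9.1 and 10.4.2.9.1 (elevated transaminases, rash) list subject-level categories, duration of events and time to first onset. They mention no rate.

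The OLE Safety Period in SAP 9.3 is "Time from the first dose of study drug in the OLE study to 28 days after the last dose of the study drug in the" extension, or to completion of study participation if that comes first.

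Entry to the extension is selective. Under Protocol 8.1.1 a subject must have completed parent-study treatment, or "Had study drug interruption(s) in the parent study, but did not permanently discontinue study drug" and attended through the last scheduled treatment visit. Protocol 8.1.2 excludes a subject with "History of drug intolerance in the parent study that would pose an additional risk to the subject in the opinion of the investigator".

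**The concern.** Long-term safety is the primary objective, and this is the only display in the plan that sets adverse events in the extension against another study. A reader will use it to ask whether harm rises or falls with longer treatment. Two features can mislead that reader.

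The first is length of follow-up. A subject percentage accumulates with time. Where no rate or common window is given, a longer column shows a higher percentage of subjects with any event even if the underlying rate is unchanged.

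The second is the cohort. Subjects who stopped study drug for good in the parent study can appear only in the parent column, and some with prior intolerance may also be absent from the extension. This can make the extension look better tolerated, and an exposure-adjusted rate does not remove it.

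The two features push in opposite directions, and the planned tables do not let a reader separate either from a real change over time.

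**Working it through.** **1. Length of the extension column**

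- Protocol synopsis, Study Duration: 96 + 96 + 4 = 196 weeks. This reproduces the stated figure.
- Cross-check: the Part B Week 96 target is Day 1345 (SAP 9.3), and dosing runs to the evening before that visit (Protocol Table 3-2), so the last dose is on Day 1344. (1344 + 28) / 7 = 1372 / 7 = 196.0 weeks.
- Part A alone: the Week 96 target is Day 673, so the last dose is on Day 672. (672 + 28) / 7 = 100 weeks.

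These are upper limits. Under Protocol 9.1.2 a subject who moves to another qualifying regimen within 28 days has no Safety Follow-up Visit, so the period ends earlier.

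**2. Which outputs carry an exposure-adjusted rate (SAP 10.4.2.1 and 10.4.2.9.1; Part A sections parallel)**

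| Output | Rate planned? |
|---|---|
| All TEAEs; Grade 3/4; related; serious; related serious; leading to discontinuation, interruption or death | Yes |
| By maximum severity | No, expressly excepted |
| By strongest relationship | No, expressly excepted |
| Grouped transaminase events and grouped rash events | None specified |

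**3. Illustration of the length effect**

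The parent length is not in the documents, and neither is any event rate. Both are assumed here. Take a constant first-event rate r per patient-year, the same in both studies, with every subject followed for the full period. The percentage with at least one event by week w is 100 × (1 − exp(−r × w / 52.18)).

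With r = 0.2, the extension column at 196 weeks is 100 × (1 − exp(−0.751)) = 52.8%, and the Part A column at 100 weeks is 31.8%.

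| Assumed parent length (weeks) | Parent column | 52.8% (196 weeks) over parent | 31.8% (100 weeks) over parent |
|---|---|---|---|
| 12 | 4.5% | 11.8 | 7.1 |
| 24 | 8.8% | 6.0 | 3.6 |
| 48 | 16.8% | 3.1 | 1.9 |
| 96 | 30.8% | 1.7 | 1.0 |

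Ratios use unrounded percentages. The true rate ratio is 1.0 in every row, which is what an exposure-adjusted rate would show. With r from 0.05 to 1.0 and parent lengths from 12 to 96 weeks, the ratio for 196 weeks runs from about 15.0 down to about 1.2.

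**4. Where that formula applies**

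It describes a percentage that can only accumulate, such as subjects with any grouped rash event or subjects in the top severity level. The maximum-severity and strongest-relationship summaries place each subject in one level. With longer follow-up subjects move up, so the lower levels can fall at constant rates. Those two summaries are still not comparable across unequal follow-up, but the table above does not size the effect for their lower levels.

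**5. The two cohorts**

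- Extension column: subjects dosed in the extension, hence no permanent discontinuers from the parent study and possibly fewer subjects with prior intolerance.
- Parent column: described only as AE data from the parent study, with no restriction to rollover subjects.

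For pulmonary exacerbations, SAP 9.2 and 9.3 state how subjects who did not enter the extension are handled. Nothing equivalent is written for adverse events. The documents give 64 subjects enrolled in the extension (SAP 7.2) but not the number treated in the parent study, so the selection effect cannot be sized.

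**The case against.** The strongest reply is that the plan already answers the main question. A reader might infer that severe or related events will be compared only as raw percentages. The documents do not support that: Grade 3/4, related, serious and related serious events, and those leading to discontinuation, interruption or death, all keep the rate. That stands, and it confines the length problem to the three summaries in step 2.

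The exception also has a reason. An event rate does not fit a table that puts each subject in one level. That stands too, and it is why a common window suits those two summaries better than a rate.

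A reader might also infer that the special-interest summaries give subject counts alone. They do not: duration and time to onset are planned, and the individual preferred terms have rates elsewhere. What is missing is a rate for the grouped events. The SAP also does not say whether these summaries fall within the side-by-side permission.

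The display is optional, descriptive and untested, and total extension exposure in patient-years is reported. This lowers the stakes but does not make unequal columns comparable.

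Finally, selection of completers is openly part of an extension design. A reader might infer that any fall in AE rates must be partly selection. The documents do not show this, because the number who did not roll over is not given and could be too small to matter.

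**Conclusion.** The point holds in a limited and conditional form. If the maximum-severity, strongest-relationship or grouped special-interest summaries are shown beside the parent study, they compare raw subject data over up to about 196 weeks (about 100 for Part A) with a follow-up of a different length. That the parent follow-up is shorter is an inference from the extension design, since no figure is given. The size of the distortion therefore cannot be computed from the documents, and the ratios in the working are illustrations under assumed rates and lengths.

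The cohort difference applies to every side-by-side AE table, including those with rates. Its likely direction is to favour the extension column, and its size is unknown and possibly nil.

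No test or formal conclusion depends on this. It is an inexpensive improvement to a primary-objective display.

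**What to change.** (a) In SAP 10.4.1.9.1 and 10.4.2.9.1, add exposure-adjusted event rates for the grouped transaminase events and the grouped rash events.

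(b) In 10.4.1 and 10.4.2, state that the maximum-severity and strongest-relationship summaries are shown beside the parent study only over a common follow-up window equal to the parent treatment duration. Otherwise, do not show those two side by side.

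(c) Wherever a side-by-side AE table is produced, add a parent-study column restricted to subjects in the OLE-SS, next to the full parent column.

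The cost is a few sentences in the SAP and slightly wider tables. All the data are already collected, and no visits or subjects are added.
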